#### **9.3.2.2     Secondary outcomes**

In order to estimate the QoL of patients with IPF according to predicted FVC% through the SGRQ and EQ-5D-5L questionnaires and the Barthel index.

- Health-related quality of life (QoL) will be investigated with the St George's Respiratory Questionnaire (SGRQ) and the EQ-5D-5L questionnaire. Quality of life will be assessed at visits T0, T6 and T12.

(See section [9.7.1](#))

In order to explore the determinants of costs and QoL in patients with IPF according to FVC % predicted level, the following variables will be collected in the CRF at visit T0 and T12:

- Sociodemographic variables: age, gender, employment, net incomes (T0).
- Anthropometric variables: weight, height and BMI (T0).
- Characteristics of IPF: date of IPF diagnosis (T0), FVC (ml) (T0, T6, T12), FVC % predicted (T0, T6 and T12), FVC rate change by year (T0 and T12), DLCO (T0, T6 and T12), the Barthel Index (T0, T6 and T12), 6MWD (T0 and T12), concomitant diseases

 Direct costs: cost incurred for medical products and services used for the prevention, detection, and treatment of a disease.

 Indirect costs: costs incurred from missing work which is loss of productivity

Proprietary confidential information © 2017 Boehringer Ingelheim International GmbH or one or more of its affiliated companies

related to IPF (T0, T6 and T12), pharmacological and non-pharmacological treatments related to IPF (T0, T6 and T12).

- Smoking status (T0, T6 and T12).
- Work with animals (now or in the past) (T0)
- Use of formal and/or informal caregiver (T0, T6 and T12).

The number of exacerbation (5) events observed during the study period will also be explored for the cost and QoL determinants.

In order to characterize acute IPF exacerbations (5) during one year according to FVC % predicted level at one year, the following variables will be collected in the eCRF along the study (12 months).

- Acute exacerbation related resource use: primary and secondary care visits, outpatient visits, emergency visits (primary care and hospital), hospitalizations, ICU with and without intubation, outpatient tests and other examinations, use of transport, use of formal and informal caregiver, pharmacological and non-pharmacological treatments (except treatments administered in hospitalization), orthopedic material, formal social services, economic aid and structural adaptations.
- Acute exacerbation related days off work

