- Economic aid and formal social services (T12, acute exacerbations)
- Structural adaptations (change in the structure of housing, elevators on the stairs in common areas, complementary technical aids, vehicle adaptation, other) (T12, acute exacerbations).

Calculation of direct health costs

Visits: The cost of visits will be calculated by multiplying the number of visits (emergency, medical) by the corresponding unit cost, which will depend on the health care area (primary or secondary) in which the visit occurred.

Hospitalizations: To calculate the cost of hospitalizations, days of stay in each unit (ICU, ward) will be multiplied by the unit cost corresponding to each unit. The sum of the costs of each service will then be calculated. In addition, emergency room admission will be added: if length of emergency stay was “less than 24 hours”, emergency room visit cost will be considered; if length of emergency stay was “more than 24 hours”, one day of emergency stay cost will be considered. Data on intubation during hospitalization (yes/no) will be used as qualitative information and not calculated as a cost.

Outpatient tests and non-pharmacological treatment: The cost of outpatient tests and non-pharmacological treatment will be obtained by multiplying the natural units of resource use (number of tests) by the unit cost of each outpatient test.

Pharmacological treatment: The costs of pharmacological treatment will be calculated taking into account:

- **Pharmacological doses**

The total dose prescribed of each active ingredient during the last 6 months will be calculated by multiplying the dose prescribed by the time on treatment. The time on treatment will be determined according to the start and end date of treatment. The scheduled dose may be daily, twice a day, three times a day, alternate days, weekly, every 2 weeks, monthly or on demand. If the schedule dose is ‘*on demand*’ an average dose according to the technical data sheet will be calculated.

The calculations described above will provide the total dose that each patient has received for the observational period.

- **Costs**

For treatments dispensed in the pharmacy office, the unit costs for each treatment were calculated taking into account the retail price (RRP) plus value added tax (VAT). From the National Health System (NHS) perspective, the co-payment of the Spanish Royal Decree-Law 16/2012 will be applying:

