- Reduced contribution medication: 10% of the retail price for medication belonging to ATC groups qualifying for reduced contribution, with a maximum contribution expressed in euros. For reduced contribution medicines with a maximum of €4.26 per package.
- Normal contribution medicines: copayment in this medicines group should be applied according to each individual situation and on declared annual income:

Medicines Co-payment	
Annual resident tax declaration	Patient's copayment
Income \geq 100.000 €	60%
Income 18.000-100.000 €	50%
Income $<$ 18.000 €	40%
Pensioners	10%
Civil servant	30%

The cost of each pharmacological treatment will be obtained by multiplying the total dose (taking into account the prescribed dose and the administration schedule) each patient has received for the observational period by the unit cost of each treatment. If the commercial brand and presentation are available, the unit costs will be those that correspond to the said commercial brand and presentation. If this information is not available, an average cost will be calculated taking into account all commercialized presentations.

The annual direct health cost will be calculated as the sum of the costs of medical visits, emergency room visits, hospital admissions, outpatient tests, non-pharmacological treatments, and pharmacological treatments.

Calculation of direct non-health costs

Transport: The cost of ambulances will be obtained by multiplying the number of trips made per unit cost. For journeys by taxi, the kilometres recorded for each journey will be multiplied by the total cost of journeys made during the observation period, and the result will be multiplied by the corresponding unit cost.

Paid caregivers: The cost of paid caregivers will be calculated by multiplying the number of hours per day of care given by the number of days. The result will be the number of hours of paid care during the observational period, and will be multiplied by the corresponding unit cost.

Orthoprosthetic material: The cost of technical aids will be calculated by multiplying the number of days the patient has required the aid by the daily cost, calculated according to the catalogues of orthoprosthetic benefits of the autonomous communities.

Financial aid and social services: The cost registered in the eCRF will be considered. The monthly cost will be multiplied by the time aid was received. If the monthly amount is 'unknown', the mean cost of patients with full data will be used.

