Structural changes: The cost registered in the eCRF will be considered.

Direct non-health costs will be calculated as the sum of transport costs, paid caregivers costs, orthoprosthetic material costs, financial aid and social services costs, and structural changes costs.

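### The societal total counts economic aid as a cost; where that aid is a money benefit it is a transfer, and a recipient's total is overstated by up to the aid amount

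*SAP*

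**What the plan says.** SAP 5.2.5 puts economic aid and formal social services on one line among the direct non-health costs. Under the calculation of those costs it says: "Financial aid and social services: The cost registered in the eCRF will be considered". The next sentences make the amount recurrent, "The monthly cost will be multiplied by the time aid was received", and fill gaps: "If the monthly amount is 'unknown', the mean cost of patients with full data will be used".

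Neighbouring items are priced by use, with no reference to who pays:
- **Paid care** is daily hours times days, and then "The result will be the number of hours of paid care during the observational period, and will be multiplied by the corresponding unit cost".
- For **orthoprosthetic material** it is days of use times a daily catalogue price.
- **Structural adaptations** are taken as entered: "Structural changes: The cost registered in the eCRF will be considered".

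The subtotal joins them: "Direct non-health costs will be calculated as the sum of transport costs, paid caregivers costs, orthoprosthetic material costs, financial aid and social services costs", plus structural changes. SAP 5.2.6.1 forms the societal total from direct health costs (without co-payment), this whole subtotal and indirect costs. Only the NHS perspective is limited by payer, to the part that the NHS finances.

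Protocol 9.3.2.1 lists economic aid within IPF-related resource use, and Protocol 9.7.1 lists it within annual direct costs. SAP 5.3 declares no changes to the planned analyses.

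**The concern.** In a societal costing, money that passes from a public body to a patient leaves one member of society and reaches another. Nothing is used up until the patient spends it, and the resource bought is then the cost. Adding the payment itself counts as consumption something that is not. If the money pays for a caregiver whose hours are already priced, the same care appears under two names.

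The societal total is one of the two results that the SAP plans for the primary objective, and it is compared across three FVC groups. An item that inflates some patients' totals without any resource use affects the level of the reported cost of illness, and could affect the group differences.

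**Working it through.** The documents give no aid amount, unit cost, expected total or share of patients on aid, so there is no planned figure to reproduce. The check traces the SAP's cost sum and then sizes it with assumed amounts.

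**Step 1: the sum in the SAP (5.2.5, 5.2.6.1).** Write H for direct health cost, I for indirect cost, A for money aid and S for in-kind social services. Let D be the full cost of adaptations and g the part of D that aid paid and that was left out of the eCRF amount, with g between 0 and A.
- Planned total = H + transport + paid care + material + (A + S) + (D − g) + I
- Resources used = H + transport + paid care + material + S + D + I
- Difference = A − g

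If adaptations are recorded gross of aid (g = 0), the overstatement is the full A. If aid went to adaptations recorded net, it is smaller. The SAP does not say which applies, hence *up to* the aid amount.

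**Step 2: size per recipient.** These are assumed amounts, for 12 months with g = 0.
- 100 × 12 = 1,200 euros
- 300 × 12 = 3,600 euros
- 600 × 12 = 7,200 euros

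**Step 3: is double counting a further error?** Let a share f of A be spent on paid care or material already costed. Then f × A duplicates a costed item and (1 − f) × A is a pure transfer. Their sum is A for every f. As an illustration, assume paid care of 8,000, adaptations of 1,000 recorded gross, and aid of 300 per month. The SAP sum for these items is 8,000 + 1,000 + 3,600 = 12,600 euros, against 9,000 euros of resources. The excess is 3,600 euros at f = 0, 0.5 or 1. Only its label changes.

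**Step 4: weight of one recipient in a group mean.** Group sizes are those expected in Protocol 9.5 and SAP 4.2. The aid is 3,600 to 7,200 euros, as assumed above.
- FVC <50%, 10–22 patients: 3,600/22 = 164 euros to 7,200/10 = 720 euros
- FVC >80%, 43–76 patients: 3,600/76 = 47 euros to 7,200/43 = 167 euros

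**Step 5: effect on a group difference.** With the same aid amount per recipient, the difference in means shifts by (p1 − p3) × A, where p1 and p3 are the shares receiving aid at FVC <50% and FVC >80%.
- p1 = p3: no shift
- 30% against 10% (assumed): 0.20 × 3,600 = 720 to 0.20 × 7,200 = 1,440 euros
- 50% against 10% (assumed): 0.40 × 3,600 = 1,440 to 0.40 × 7,200 = 2,880 euros
- Higher receipt at FVC >80% would reverse the sign.

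The documents give neither p1 nor p3.

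**The case against.** The strongest reply is that the documents never say what the aid is. It shares a line with formal social services, which are real resources and belong in a societal total. A monthly amount could also be payment for a service. This stands in part: the overstatement covers only the portion that is a money benefit, and that portion is unknown. However, the protocol lists economic aid and formal social services as separate items, and the SAP speaks of financial aid with a monthly amount received. The natural reading is that at least some of the line is money paid to the patient.

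Three stronger readings are tempting, and the documents do not support them.
- **Contradiction with the protocol's definition of direct cost.** Footnote 5 in Protocol 9.3.2 reads "Direct costs: cost incurred for medical products and services used for the prevention, detection, and treatment of a disease". The word *medical* makes it too narrow to single out aid: read literally, it would also remove transport, paid caregivers and social services. SAP 5.2.5 has its own, broader category of direct non-health cost. The footnote is no argument here.
- **Double counting on top of the transfer error.** Step 3 shows that it is the same euros. Overlap is clear on the text only for items priced in full (paid care and orthoprosthetic material). For adaptations it depends on how the eCRF amount is recorded.
- **An inflated cost gradient towards low FVC.** Nothing in the documents links aid to FVC or dependency, so a distortion in either direction, or none, is possible.

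It can also be said that economic aid is a listed cost component in the protocol, that the group tests are declared exploratory, and that SAP 5.2.8 promises a description of every recorded variable, so aid may be visible in the report anyway. Listing aid shows consistent intent but does not make a transfer a resource cost. The other two points limit the harm without correcting the total.

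**Conclusion.** The point holds for the societal total. Followed as written, SAP 5.2.5 and 5.2.6.1 count any money aid as resource use, with no netting and no transfer rule. Each recipient's total is too high by up to the aid received: 3,600 to 7,200 euros per recipient-year at an assumed 300 to 600 euros per month. The full amount applies if adaptations are recorded gross of aid.

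The effect on group means and on the FVC comparison cannot be sized from the documents, because the number of recipients, their distribution across groups and the aid amounts are all missing. One recipient weighs more in the small FVC <50% group, so the matter should be settled before analysis. The NHS perspective is not at issue, because it already counts only what the NHS finances. The eCRF and diary were not available for this check and may record what the aid was for.

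**What to change.** - Split the combined line in SAP 5.2.5 into money aid and in-kind formal social services.
- Keep in-kind services in the societal total, and count any service once if it also appears as paid caregiver hours.
- Take money aid out of the societal total and report it on its own line as a transfer. Keep it in a payer view only where that payer funds it.
- State that paid care and adaptations are recorded gross of aid.
- Declare the change in SAP 5.3, because Protocol 9.3.2.1 and 9.7.1 list economic aid as a cost component.
- If the eCRF does not separate aid from services, show the societal total with and without the combined line.

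The cost is a SAP revision, a declared departure from the protocol's cost list, and a somewhat lower societal total. It may also need a data query to separate the two items. No information is lost, since aid is still reported.

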5.2.6. Indirect cost

Indirect costs are defined as the costs associated with the impact of the disease borne by the patient and will include:

- Patients' days off work along 12 months (T6, T12, acute exacerbations).
- Informal caregiver (time dedicated to patient care with IPF) (T6, T12, acute exacerbations).

The calculation will be based on the human capital method, assuming that the wage/salary reflects the productivity of the worker. The opportunity cost method will be used to calculate informal care costs. The indirect costs will be estimated by applying salary costs based on the latest data published by the Spanish Instituto Nacional de Estadística (INE) from the salary structure survey, adjusted to age. With this method, the indirect cost of patients/caregiver not actively employed during the study period (e.g., unemployed and retired workers) will be 0.

5.2.6.1 Total cost

In the analysis from the social perspective, the total costs will be obtained as the sum of the direct health costs (without co-payment), direct non-health costs and indirect costs.

In the analysis from the perspective of the Spanish NHS, health costs will be direct health costs and direct non-health cost considering only the part financed by the NHS.

5.2.6.2 Unit cost

The following unit costs and cost data sources will be used:

- Hospitalizations, emergency room visits, medical visits, outpatient tests, and non-pharmacological treatments: the unit costs will be established from the representative national rates collected in the ESALUD Spanish health costs database.
- Pharmacological treatments: prices published in the Drug Database of the General Council of Official Associations of Pharmacists.
- Lost productivity: wage/salary costs will be calculated according to the latest data published by the Spanish National Statistics Institute on the survey of the salary structure.

In order to obtain the most recent unit costs, they will be consulted at the time of the analysis. All costs will be expressed in euros for the year in which the analysis is performed, updating as necessary the costs from previous periods according to the cumulative consumer price index (CPI).

For the primary objective of the study, the characteristics of the subpopulations defined by the categorisation of the deterioration in predicted FVC (FVC <50%, FVC 50-80%, FVC >80%) at the time of inclusion (T=0) will be described by means of: mean, SD, 95% CI of the mean, median, IQR (P25-P75), max. and min. The CI of the costs will be calculated using bootstrapping techniques using replacement samples of the same size as the original sample. In total 10 000

simulations will be made and the 2.5 and 97.5 percentiles of the distribution will be used to determine the 95% CI.

Analysis of variance (ANOVA) or Kruskal-Wallis tests will be performed to compare the direct and indirect costs by subpopulation (FVC <50%, FVC 50-80%, FVC >80%). Results of all statistical tests must be interpreted purely exploratorily.

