### **9.7.1 Main analysis**

*a)* To compare the economic impact of Idiopathic Pulmonary Fibrosis (IPF) according to predicted FVC% (FVC<50%, FVC 50-80%, FVC>80%), in adult patients through the estimation of annual direct and indirect costs associated with the disease.

Annual direct IPF-related costs (primary and secondary care visits, outpatient visits, emergency visits -primary care and hospital-, hospitalisations, ICU with and without intubation, outpatient tests and other examinations, pharmacological and non-pharmacological treatments, orthopedic material, use of transport, formal caregiver, formal social services, economic aid and structural adaptations) and indirect costs (days off work and informal caregiver) will be quantified for each patient over the follow-up period of 12 month.

The direct costs over the 12 month follow-up period will be quantified by multiplying the recorded natural units of use of resources by the unit costs obtained by consulting Spanish databases or similar studies. The opportunity cost method will be used to calculate informal care costs. The indirect costs will be estimated by applying salary costs based on the latest data published by the Spanish Instituto Nacional de Estadística (INE) (6) from the salary structure survey, adjusted to age.

In order to obtain the most recent unit costs, they will be consulted at the time of the analysis. All costs will be expressed in euros for the year 2018, updating as necessary the costs from previous periods according to the cumulative consumer price index (CPI) since the publication of the cost up to December 31, 2017.

For the primary objective of the study, the characteristics of the subpopulations defined by the categorisation of the deterioration in predicted FVC (FVC <50%, FVC 50-80%, FVC >80%) at the time of inclusion (T=0) will be described. The Chi-square test will be used for the comparisons of the qualitative (categorical) variables. For the comparisons of the quantitative (continuous) variables, analysis of variance (ANOVA) or Kruskal-Wallis tests will be performed. Results of all statistical tests must be interpreted purely exploratorily.

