3. STUDY OBJECTIVES

3.1. PRIMARY OBJECTIVE

To compare the economic impact of Idiopathic Pulmonary Fibrosis (IPF) according to forced vital capacity (FVC) % predicted level (FVC<50%, FVC 50-80%, FVC>80%), in adult patients through estimation of annual direct and indirect costs associated with the disease during one year.

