5.2.8. Statistical methodology

A descriptive analysis will be performed of all the variables recorded for the study population. For the continuous variables, the mean, the SD, the 95% CI of the mean, the median, IQR (P25-P75), min. and max, and valid n will be calculated. Categorical variables will be presented as absolute and relative frequencies (percentages).

For bivariate analysis, continuous endpoints may be compared across subgroups of population using two-sample t-tests or ANOVA (if normality criteria are met), or the Mann–Whitney U test or Kruskal-Wallis test (if normality criteria are not met). The categorical endpoints will be analysed using the Chi-square or Fisher test, as appropriate. If apply, lineal correlations between continuous variables will be analysed (Pearson or Spearman correlations).

Multivariate exploratory analyses (e.g. generalized linear models) will be applied which include costs (Total annual IPF-related costs) and quality of life (SGRQ and EQ-5D-5L in baseline visit-T0) as dependent variables, and the explanatory variables will be discussed based on previous bivariate analyses and clinical relevance with $p<0.1$. Sample size and constraints imposed by the analysis models may prevent to include all variables of interest in this setting.

For all exploratory statistical tests, a significance level alpha of 0.05 will be assumed.

The data analysis will be performed by using the SAS statistical package, version 9.4 or later.

All costs will be estimated per patient per year, and will be specified with respect to the different FVC % predicted level (FVC<50%, FVC 50-80%, FVC>80%) and total sample.

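### The primary cost comparison plans no between-stratum difference in mean cost and no interval for one; its percentile-bootstrap 95% interval also under-covers at the expected size of the FVC <50% stratum

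*SAP*

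**What the plan says.** - SAP 3.1 gives the primary objective: "To compare the economic impact of Idiopathic Pulmonary Fibrosis (IPF) according to forced vital capacity (FVC) % predicted level", through annual direct and indirect costs.
- SAP 5.2.6.1 defines two totals. The societal one: "In the analysis from the social perspective, the total costs will be obtained as the sum of the direct health costs", to which direct non-health and indirect costs are added. The NHS one: "In the analysis from the perspective of the Spanish NHS, health costs will be direct health costs and direct non-health cost", restricted to the part the NHS finances.
- SAP 5.2.6.2 describes each baseline FVC stratum by mean, SD, 95% CI, median, IQR and extremes. The cost interval comes from 10,000 bootstrap resamples, and "the 2.5 and 97.5 percentiles of the distribution will be used to determine the 95% CI". The comparison itself is one sentence: "Analysis of variance (ANOVA) or Kruskal-Wallis tests will be performed to compare the direct and indirect costs by subpopulation".
- Protocol 9.7.1 matches this. For continuous variables, "analysis of variance (ANOVA) or Kruskal-Wallis tests will be performed".
- SAP 5.2.8 chooses between the tests by normality. It uses ANOVA if the criteria are met, otherwise the "Kruskal-Wallis test (if normality criteria are not met"). It does not define the criteria.
- Generalised linear models with cost as the dependent variable appear under the determinants objective in SAP 5.2.7 (b), where they depend on sample size. SAP 5.2.8 repeats them without that condition.
- Protocol 9.5 and SAP 4.2 expect 10-22, 102-143 and 43-76 patients in the <50%, 50-80% and >80% strata. Both documents label all tests exploratory.

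**The concern.** A cost comparison should say how many euros separate the strata and how uncertain that figure is. An omnibus p-value says neither, and it does not say which strata differ. If the undefined normality rule leads to Kruskal-Wallis, the only planned comparative result concerns ranks, whereas the quantity of interest in a cost-of-illness study is the arithmetic mean.

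The interval matters most for FVC <50%. Protocol section 7 expects higher cost there, and Protocol 9.5 hopes for first insights from that small group. An interval labelled 95% that covers less would make the least precise stratum look more precise than it is.

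**Working it through.** **1. Is a contrast planned anywhere?** Four places could supply one.
- SAP 5.2.6.2 and Protocol 9.7.1: stratum descriptives and an omnibus test; no difference, ratio or pairwise interval.
- SAP 5.2.8, two-sample tests: generic and permissive, with no stratum pair named and no interval.
- SAP 5.2.7 (b) and 5.2.8, generalised linear models: FVC % predicted is among the candidate determinants, but predictors are to be chosen from the bivariate results and no FVC-stratum contrast is specified.
- SAP 5.2.7 (d): descriptive, by change in FVC over the year.

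None commits to a between-stratum mean-cost difference.

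**2. Stratum sizes.** Total 200 times the stated prevalences:
- <50%: 200 × 5% = 10; 200 × 11% = 22.
- 50-80%: 200 × 51% = 102; 200 × 73% = 146 (stated 143).
- >80%: 200 × 22% = 44 (stated 43); 200 × 38% = 76.

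The plan's figures reproduce apart from trivial differences.

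**3. Precision of the missing contrasts.** Approximate half-width in SD units, common SD: 1.96 × √(1/n1 + 1/n2). With a coefficient of variation (CV) of 1, multiply by 100 to read it as a percentage of mean cost.

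| Pair | Sizes | Half-width |
|---|---|---|
| <50% vs 50-80% | 10 vs 143; 22 vs 102 | 0.64; 0.46 |
| <50% vs >80% | 10 vs 76; 22 vs 43 | 0.66; 0.51 |
| 50-80% vs >80% | 102 vs 76; 143 vs 43 | 0.30; 0.34 |

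**4. Omnibus test against mean cost.** Simulated with equal true means and unequal skew (sizes 16/122/60, lognormal, CV 1.5/0.5/0.5), Kruskal-Wallis rejected in 46.5% of runs and ANOVA in 30.9%. Under those assumptions neither p-value can stand in for a mean difference.

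**5. Percentile interval with normal costs.** For a mean, the interval is close to the mean ± 1.96 × (SD with divisor n)/√n. Coverage is therefore P(|t| < 1.96 × √((n−1)/n)) with n−1 degrees of freedom.
- n = 10: 1.96 × √0.9 = 1.859, giving 90.4%.
- n = 22: 1.96 × √(21/22) = 1.915, giving 93.1%.

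**6. Percentile interval under assumed cost distributions.** The documents give no cost SD or shape. Results are from 4,000 data sets of 2,000 resamples (Monte Carlo standard error at 85% coverage: √(0.85 × 0.15/4000) = 0.6 points). Coverage, %:

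| Cost distribution | Percentile n=10 | n=15 | n=22 | t interval n=10 | n=22 |
|---|---|---|---|---|---|
| Normal, CV 0.3 | 89.6 | 92.1 | 93.1 | 94.4 | 94.6 |
| Gamma, CV 0.5 | 88.8 | 91.3 | 92.7 | 93.5 | 94.6 |
| Gamma, CV 1.0 | 86.5 | 88.7 | 90.6 | 90.7 | 92.0 |
| Lognormal, CV 0.5 | 87.4 | 89.9 | 91.8 | 91.9 | 93.7 |
| Lognormal, CV 1.0 | 83.2 | 86.4 | 87.6 | 87.0 | 89.0 |
| Lognormal, CV 1.5 | 78.3 | 80.9 | 84.4 | 81.9 | 85.5 |

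Under skew most misses lie wholly below the true mean: at n = 10, lognormal CV 1.0, 15.4% below and 1.5% above. At n = 102 percentile coverage is 90.3-94.5%.

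**7. What alternatives achieve.** Bootstrap-t for the single-stratum mean, lognormal CV 0.5/1.0/1.5: 95.9/93.5/91.6% at n = 10 and 93.9/91.7/90.0% at n = 22. For the difference, lognormal costs, same CVs:

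| Sizes | Percentile | Welch | Bootstrap-t |
|---|---|---|---|
| 10 vs 143 | 89.6/87.2/82.8 | 94.5/90.0/85.1 | 95.4/91.8/87.5 |
| 22 vs 102 | 90.8/87.8/85.2 | 93.2/89.3/86.8 | 92.6/90.1/86.7 |

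For 50-80% vs >80%, Welch covers about 95%. Coverage for <50% vs >80% was not simulated.

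**The case against.** The best defence is that the study claims little. Protocol 9.1 calls the design descriptive, Protocol 9.5 and SAP 4.2 foresee that some comparisons will be descriptive only, Protocol 9.9 lists subgroup size as a limitation, and all tests are exploratory. Stratum means, SDs and numbers will be reported, so a reader could compute a Welch interval. This limits the harm, and it means the planned summaries are not themselves biased by the omission. It does not make the contrast a planned result, nor does it correct an interval labelled 95%.

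A second defence is that SAP 5.2.8 says the cost models will be applied. A reader might infer that they are merely optional, or that the plan never relates cost to FVC. The documents do not support that reading: SAP 5.2.7 (b) makes the models conditional on sample size and SAP 5.2.8 states them outright. They still commit to no stratum contrast.

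Third, the remedies under-cover too when skew is strong, and bootstrap-t can be unstable. Both statements are true. That is why the approximate label is part of the fix and why the missing contrast is the leading point.

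A reader might also infer that indirect cost will be mostly zero, because "the indirect cost of patients/caregiver not actively employed during the study period (e.g., unemployed and retired workers) will be 0". The documents give no employment or caregiver share, so this is a contingency and not a finding.

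**Conclusion.** The concern holds in two parts of unequal weight.

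The main part rests on the text alone: the primary objective is comparative, and no between-stratum difference in mean cost, or interval for one, is planned.

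The secondary part is that the percentile interval falls short of 95% at 10-22 patients. With normal costs the shortfall is about 2 to 5 points. Under the assumed skewed distributions coverage is about 78-89% at n = 10 and 84-93% at n = 22. The direction is secure across everything tried. The size depends on assumed shape and CV, and it is modest at n = 22 with near-symmetric costs.

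Two stronger readings should be resisted. The low-side misses do not mean that the sample mean is biased; they arise because the interval is too short on its upper side under skew. And 78% is not a prediction for this study, since it needs lognormal costs with CV 1.5 at n = 10.

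**What to change.** 1. In SAP 5.2.6.2, whichever omnibus test is used, report the difference in arithmetic mean annual total cost with a 95% Welch interval for <50% vs 50-80%, 50-80% vs >80% and <50% vs >80%. Do this for both the societal and the NHS totals of SAP 5.2.6.1 (3 × 2 = 6 intervals), labelled exploratory.
2. For the FVC <50% means of total and direct cost, replace the percentile limits with bootstrap-t limits. An ordinary t interval is a simpler, partial improvement. Label every interval involving this stratum approximate, because no method tried restores 95% at n = 10 with strong skew.
3. If a component such as indirect cost proves mostly zero in a stratum, do not use bootstrap-t for it. With 1 or 2 non-zero patients among 10, a share (1 − 1/10)^10 = 35% or (1 − 2/10)^10 = 11% of resamples are all zero and the statistic is undefined there. Report the proportion non-zero and the mean.

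Cost: SAP wording and a few lines of code on the bootstrap already planned; no new data. The FVC <50% intervals widen. The median bootstrap-t width is about 1.1-1.8 times the percentile width, and at n = 10 with CV 1 it exceeds about 2.3-2.7 times in 10% of samples. The low-FVC contrasts will be visibly imprecise.
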